14.1.3. Data Capture Methods (CRF Development and Completion)

Clinical data recorded in source documents, including the barcoded CRF pages, should be completed in a neat, legible manner to ensure accurate interpretation of data. Source documentation supporting the CRF data should document the dates and details of study procedures, AEs and subject status. The PI will ensure that all information in the CRFs and all other source documents that support the data collected from each subject are maintained in a secure area and treated as confidential material.

Data reported in the CRF that is derived from other source documents should be consistent. It is the PI's responsibility to ensure the accuracy, completeness, and timeliness of the data reported in the subject's CRF and any supporting documentation.

Clinical data entered in the barcoded CRFs and other source documents (as listed above) are uploaded to a 21 CFR Part 11 compliant EDC system using intelligent character recognition software. The scanned pages are then verified against data captured in the database by the data management staff at DFnet. For randomization, data confirming eligibility of the subject, *P.falciparum* infection status and HIV status at screening (based on source data as listed above), is entered directly into the same EDC system by site staff at Visit 2.

The database includes password protection and internal quality checks, such as automatic range checks, to identify data that appear inconsistent, incomplete, or inaccurate.

Additionally, a description of this clinical trial will be available on <http://www.ClinicalTrials.gov>, as required by U.S. Law. The clinicaltrials.gov registry will not identify any individual participants and will include a summary of the results.

14.1.4. Data Management

The PATH designated Data Management CRO, DFnet, will develop a Data Management Plan (DMP) for review and approval by PATH. The DMP will describe the roles of the stakeholders and specific procedures to ensure appropriate handling of data at all steps of the data management process, to assure a valid and high-quality database at the end of the study, ready for analysis.

14.1.5. Data Storage

All study documentation containing personal information relating to study subjects like consent forms and other documents that might link subject ID with other subject personal details will be kept in a secure locked area with limited access at the KCRC. Such documentation will only be made available to authorized personnel. These study documents will be made available to the investigators, clinical personnel who require this information to treat the subjects and the above-mentioned personnel for inspection or auditing reasons. In addition, access to subjects' medical records will be granted to representatives of the Sponsor, regulatory agencies, ethics committees, and the USAMRDC for the purpose of validating data.

14.2. Study Records Retention and Disposal

Study documents should be retained for the duration required by PATH, applicable local regulations, and in accordance to U.S. DoD requirements, in a safe and secure facility. No records will be destroyed without the written consent of PATH. Upon study completion, all records will be stored safely at one of USAMRD-A's archiving facilities or at a secure contracted storage facility for at least 15 years. If storage at an alternative facility is considered, this will be documented, and the documentation will be filed in the study's regulatory file. Should longer storage be recommended by the sponsor or relevant authorities, the site will contact the reviewing IRBs for consideration and approval. Study files can be stored either as paper or digitally. Digitization, if done, will consist of the scanning of all paper records according to site SOPs to ensure accurate and complete representation of the same. This may be done by the site staff of a contracted third-party. All digitized records will be maintained on a secure, password protected computer system with access limited to those with access to study as previously listed in this protocol as well as USAMRD-A's archivist(s) and IT personnel who will maintain the database. Upon completion of digitization of study records, and receipt of a sponsor's approval, paper copies may be destroyed by incineration according to site SOPs.

Paper or digitized records may be disposed of after storage duration has been met (15 years or as otherwise specified as above) and with the sponsor's approval. Any remaining paper records will be incinerated and/or digitized records will be securely deleted. The final disposal of any remaining paper or digitized records will be witnessed by a representative of USAMRD-A's regulatory affairs department and will be documented. The documentation of records disposal will be provided to the sponsor and a copy will be stored at the Regulatory Affairs department.

14.3. Protocol Deviations

A protocol deviation is any noncompliance with the clinical trial protocol, or GCP requirements.

The noncompliance may be either on the part of the participant, the investigator, or the study site staff.

As a result of deviations, corrective actions are to be developed by the site and implemented promptly. It is the responsibility of the site to use continuous vigilance to identify and report deviations.

14.4. Publication and Data Sharing Policy

This study will comply with PATH and U.S. DoD policies. PATH policy ensures that the public has open access to the published results of Gates Foundation funded research. The International Committee of Medical Journal Editors (ICMJE) member journals have adopted a clinical trials registration policy as a condition for publication.

The first publication or disclosure of study results shall be a complete publication or disclosure coordinated by PATH.

15. CONFLICT OF INTEREST POLICY

The independence of this study from any actual or perceived influence is critical. The sponsor, PATH has no conflict of interest to disclose.

16. STUDY LIMITATIONS AND POTENTIAL BIASES

Limitations of this study include that the ideal correlate of protection for a malaria vaccine is unknown given that antibody responses do not always correlate with protection. This study is exploring additional immunological responses to have a better understanding of the correlate of protection. Additionally, while the PCR assay used here tests for the presence of a blood stage infection, incubating liver stage parasites may be missed during screening resulting in misallocation of a subject to a group other than originally intended. We believe that such an occurrence would be rare and there is no way to mitigate should such an event would occur. The selection methods and randomization were designed to limit bias, but we may potentially have other confounding factors that were not considered and will fail to be randomly distributed despite our best efforts.

17. MILITARY RELEVANCE

US Service Members conduct operations in regions of the world where they are at risk of malaria acquisition. Acquiring malaria is significantly detrimental to individual Service Members and their units resulting in lost duty hours, increased utilization of medical resources in the field (often in austere settings), potential requirement for medical evacuation, risk of death to individual Service Members, and risk to a unit's mission if a significant proportion or key individuals become ill. As such medical countermeasures to malaria are essential in malaria endemic regions and include effective treatment, effective prophylaxis, and immunoprophylaxis (such as a vaccine). Malaria vaccines have the advantage of potentially eliminating the need for other prophylaxis (if high enough efficacy) and/or decreasing the severity of disease if an individual does become ill. To date, the RTS,S malaria vaccine is the most advanced in development and has shown reasonable efficacy in adults in challenge studies, but less so in field settings. This study attempts to optimize the RTS,S vaccines protective efficacy in endemic areas

and also further understand the immunology of a protective response. What is learned will help in advancing the understanding and application of this vaccine, and in the future development of malaria immunoprophylaxis. Additionally, an effective malaria vaccine may contribute to disease reduction in the long-term goals of malaria elimination. In the short term, reduced disease burden can improve the health of individuals in endemic regions which can improve regional stability. Also, any declines in malaria burden as we work toward elimination decreases the risk to service members deployed in endemic areas.

19. APPENDICES**APPENDIX A. SCREENING VISIT PROCEDURES**

Screening Visit	1
Type of Visit (KC = KCRC Clinic Visit or FV = Field visit)	KC
Study day	-39 to -28
Informed consent	•
Photo for ID card	•
Demographics	•
Medical History	•
Physical Examination	•
Concomitant medications	•
Check inclusion/exclusion criteria	•
Vital Signs (BP, pulse, temperature)	•
Urine Pregnancy test	•
Complete blood count (Hb, WBC, PLT; (4 mL)	•
Creatinine, ALT (4 mL)	•
HIV (4 mL)	•
Blood sampling for assessment of parasitemia (PCR and DBS) (0.35 to 0.5 mL) by finger stick	•
Record any SAEs	•
CUMULATIVE BLOOD VOLUME	13 mL

APPENDIX B. EPOCH 1: TREATMENT AND IMMUNIZATION PHASE

Visit #	Treatment and Immunization Phase (Epoch 1)																
	2	3^	4^	5	6	7	8^	9^	10^	11	12 ¹	13	14^	15^	16^	17	18 ¹
Type of Visit (KC or FV) preferred	KC	FV	FV	KC	KC	KC	KC	FV	FV	KC	FV	KC	KC	FV	FV	KC	FV
Study day	-27	-26	-25	1	2	8	15	16	17	29	36	57	190	191	192	197	204
Permissible window (+/- days)*	2	0	0	3	0	+2	2	0	0	3	+2	3	2	0	0	3	+2
Issue subject's identification card	•																
Check inclusion/exclusion criteria	•			•			•			•			•				•
Record any intercurrent medical conditions	•			•			•			•			•				•
Record any concomitant medications/vaccinations	•			•	•	•	•	•		•		•	•				•
Record if subject belongs to reactogenicity sub-cohort ¹	•																
Check contraindications to vaccinations/anti-malarial medications	•			•			•			•			•				•
History of fever/Record body temperature	•			•			•			•			•				•
Focused/Symptom & physical exam as needed				•						•							•
DHA/piperaquine	•	•	•				•	•	•								
Primaquine (low dose)	•						•					•					
Coartem												•	•	•			
Record vital signs (BP, pulse, temperature)				•						•							•
Randomization upon completion of parasite PCR	•																
Vaccination				•						•							•
LABS																	
Complete blood count (Hb, WBC, PLT; 4 mL)				•													
Creatinine, ALT (4 mL)				•													
Hemoglobinopathy screen (4 mL)	•																
Urine Pregnancy test	•			•			•			•			•			•	
Buccal swab- HLA typing (Groups 1, 2, 3 only)	• ³																

Visit #	Treatment and Immunization Phase (Epoch 1)																
	2	3^	4^	5	6	7	8^	9^	10^	11	12 ¹	13	14^	15^	16^	17	18 ¹
Type of Visit (KC or FV) preferred	KC	FV	FV	KC	KC	KC	KC	FV	FV	KC	FV	KC	FV	FV	KC	FV	
Study day	-27	-26	-25	1	2	8	15	16	17	29	36	57	190	191	192	197	204
SAFETY DATA COLLECTION ¹																	
Record solicited local & systemic AEs				●	●	●				●	●					●	●
Record unsolicited AEs post anti-malarial treatment/ post vaccination	●	●	●	●	●	●	●	●	●	●	●	●	●	●	●	●	●
Record AEs/SAEs (fatal; AESI)	●	●	●	●	●	●	●	●	●	●	●	●	●	●	●	●	●
INVESTIGATIONAL ASSAYS																	
Blood serum sampling (10 ml) -refer to Appendix F for Group-specific timepoints ²	●			●						●		●				●	
CMI- PBMC from all RTS,S vaccinated subjects Groups 1,2,3 (30 mL)	●			●		●											
Whole blood transcriptomics all subjects (Paxgene; < 3 mL)	●			●	●	●											
PARASITEMIA ASSESSMENT																	
Blood sampling for PCR and DBS (0.35 to 0.5 ml)				●						●						●	
CUMULATIVE BLOOD VOLUME (mL)	60			112	115	158				169		179				190	

* Rationale for window period: Anti-malarial treatment does not allow for missed doses (no permissible window period). Total 6-day window period on either side of optimal vaccination scheduled day (+/- 3d). total 8-day window period on either side of ADI scheduled days (+/- 4 days)

¹ Reactogenicity cohort for solicited local and general AEs are the first 50 subjects per group in Groups 1 and 2, and all subjects in Group 3 (Field Visits 12 and 18 are only applicable to this cohort). All subjects (Groups 1 to 5) will have unsolicited AEs captured through day 28 after each immunization and post anti-malarial treatment, as applicable (i.e. Groups 1, 2, 4 and 5).

² Only the first 50 subjects each in Groups 4 and 5 will have blood samples collected for rabies antibody determination. Subjects in Groups 4 and 5 who do not require serology samples or follow up for solicited AEs post anti-malarial treatment or vaccination may have these visits done in the field instead of at the clinic.

³ Buccal swab samples for HLA typing should ideally be collected (for all subjects in Groups 1, 2, and 3) at Visit 2, but can be collected at a later study visit.

⁴ While subjects in Group 3 are required to attend Visit 2 for enrolment and randomization, Visits 8 and 14 for start of anti-malarial treatment, and Visits 3, 4, 9, 10, 15, and 16 for DOT of anti-malarial treatment by FW or CHW are not applicable for subjects assigned to this group.

APPENDIX C. EPOCH 2: ACTIVE DETECTION OF INFECTION PHASE

	Active Detection of Infection (Epoch 2)									
	19	20	21 [†]	22 [†]	23 [†]	24 [†]	25 [†]	26 [†]	27	
Visit #	19	20	21 [†]	22 [†]	23 [†]	24 [†]	25 [†]	26 [†]	27	
Type of Visit (KC or FV) preferred	FV	KC	FV	FV	FV	FV	FV	FV	KC	
Study day	211	225	246	267	288	309	330	351	372	
Permissible window (+/- days)*	3	4	4	4	4	4	4	4	4	
Issue subject's identification card										
Check inclusion/exclusion criteria										
Record any intercurrent medical conditions										
Record any concomitant medications/vaccinations		•								
Record if subject belongs to reactogenicity sub-cohort ¹										
Check contraindications to vaccinations/anti-malarial medications										
History of fever/Record body temperature	•	•	•	•	•	•	•	•	•	
Focused/Symptom & physical exam as needed										
DHA/piperaquine ; Primaquine (low dose)										
Coartem										
Record vital signs (BP, pulse, temperature)										
Vaccination										
SAFETY LABS										
Complete blood count (Hb, WBC, PLT; 4 mL)										
Creatinine, ALT (4 mL)										
Urine Pregnancy test										
SAFETY DATA COLLECTION ¹										
Record solicited local & systemic AEs										
Record unsolicited AEs post anti-malarial treatment/ post vaccination	•	•								

Visit #	Active Detection of Infection (Epoch 2)								
	19	20	21 [†]	22 [‡]	23 [‡]	24 [‡]	25 [‡]	26 [‡]	27
Type of Visit (KC or FV) preferred	FV	KC	FV	FV	FV	FV	FV	FV	KC
Study day	211	225	246	267	288	309	330	351	372
Record AEs/SAEs (fatal; AESI)	●	●	●	●	●	●	●	●	●
INVESTIGATIONAL ASSAYS									
Blood serum sampling (10 ml) -refer to Appendix F for Group-specific timepoints ²		●							●
CMI (PBMC from RTS,S vaccinated subjects (Gps 1,2,3) only (30 mL)		●							
Whole blood transcriptomics all subjects (Paxgene; < 3 mL)		●							
PARASITEMIA ASSESSMENT									
Blood sampling for PCR and DBS (0.35 to 0.5 ml) ³	●	●	●	●	●	●	●	●	●
CUMULATIVE BLOOD VOLUME (mL)	191	235	236	237	238	239	240	241	252

* Rationale for window period: Anti-malarial treatment does not allow for missed doses (no permissible window period). Total 6-day window period on either side of optimal vaccination scheduled day (+/- 3d). total 8-day window period on either side of ADI scheduled days (+/- 4 days)

¹ Reactogenicity cohort for solicited local and general AEs are the first 50 subjects per group in Groups 1 and 2, and all subjects in Group 3. All subjects (Groups 1 to 5) will have unsolicited AEs captured through day 28 after each immunization and post anti-malarial treatment, as applicable (i.e. Groups 1, 2, 4 and 5).

² Only the first 50 subjects each in Groups 4 and 5 will have blood samples collected for rabies antibody determination.

³ Subjects in Group 3 will not participate in ADI. Parasitemia assessment is therefore not applicable for this group (with the exception of the cross-sectional sampling at Visit 27 and Study Termination).

[†] Subjects in Group 3 will not participate in ADI (as above), but will be followed up 7 and 28 days post dose 3, as per protocol i.e. Visit 18 (per Appendix B, Epoch 2) and Visit 20. Visits 19, and 21 to 26 are therefore not required for this group Visit 27 is required for group 3.

APPENDIX D. EPOCH 3: EXTENSION DETECTION OF INFECTION PHASE (IF REQUIRED)

	Active Detection of Infection-Extension (Epoch 3)							
Visit #	28	29	30	31	32	33	34	35
Type of Visit (KC or FV) preferred	FV	FV	FV	FV	FV	FV	FV	FV
Study day	393	414	435	456	477	498	519	540
Permissible window (+/- days)*	4	4	4	4	4	4	4	4
Issue subject's identification card								
Check inclusion/exclusion criteria								
Record any intercurrent medical conditions								
Record any concomitant medications/vaccinations								
Record if subject belongs to reactogenicity sub-cohort ¹								
Check contraindications to vaccinations/anti-malarial medications								
History of fever/Record body temperature	•	•	•	•	•	•	•	•
Focused/Symptom & physical exam as needed								
DHA/piperaquine ; Primaquine (low dose)								
Coartem								
Record vital signs (BP, pulse, temperature)								
Vaccination								
SAFETY LABS								
Complete blood count (Hb, WBC, PLT; 4 mL)								
Creatinine, ALT (4 mL)								
Urine Pregnancy test								
SAFETY DATA COLLECTION								
Record solicited local & systemic AEs								

	Active Detection of Infection-Extension (Epoch 3)							
Visit #	28	29	30	31	32	33	34	35
Type of Visit (KC or FV) preferred	FV	FV	FV	FV	FV	FV	FV	FV
Study day	393	414	435	456	477	498	519	540
Record unsolicited AEs post anti-malarial treatment/ post vaccination								
Record AEs/SAEs (fatal; AESI)	•	•	•	•	•	•	•	•
PARASITEMIA ASSESSMENT								
Blood sampling for PCR and DBS (0.35 to 0.5 mL)– Groups 1, 2, 4 and 5 only.	•	•	•	•	•	•	•	•
CUMULATIVE BLOOD VOLUME (mL)	253	254	256	257	258	259	260	281

* Rationale for window period: Anti-malarial treatment does not allow for missed doses (no permissible window period). Total 6-day window period on either side of optimal vaccination scheduled day (+/- 3d). total 8-day window period on either side of ADI scheduled days (+/- 4 days)

APPENDIX E. STUDY TERMINATION VISIT

Visit #	STUDY TERMINATION VISIT
Type of Visit (KC or FV) preferred	KC or FV¹
Study day	TBD²
Permissible window (+/- days)	+56 ²
Record AEs/SAEs (fatal; AESI)	●
Blood sampling for PCR and DBS (0.35 to 0.5 ml) (all subjects, all groups)	●
Blood serum sampling (10 ml) ³ : - Groups 1 to 3	●
Offer and schedule post-study course of rabies vaccination – Groups 1 to 3 only ⁴	●

¹ Either acceptable, though visits for Groups 1 to 3 will need to be conducted at KC for serology sample collection.

² Date for visit will be the day according to the criteria as specified in section 7.1.1, part E of the protocol being met; and will be completed for all volunteers within 56 days of the set calendar date.

³ Serology timepoint at Study Termination only applies to Groups 1 to 3 - see sections 7.1.1, above, and Appendix F for further details.

⁴ Rabies immunization for subjects in Groups 1, 2, and 3 when scheduled at termination visit may include any rabies vaccine approved for use in Kenya. If participants are willing/able, rabies immunization may start at this study termination visit after all study specific procedures are completed.

APPENDIX F. BIOLOGICAL SAMPLES FOR IMMUNOGENICITY TESTING

SAMPLES COLLECTED	Visit #	2	5	6	7	11	13	17	20	27	Study Termination Visit
		-									
	Study day	27	1	2	8	29	57	197	225	372	TBD*
Secondary endpoint -Groups 1, 2, 3											
Serum	anti-CS NANP levels	●	●			●	●	●	●	●	●
	anti-CS NANP avidity	●	●			●	●	●	●	●	●
	anti-CS C-term levels	●	●			●	●	●	●	●	●
	anti-CS C-term avidity	●	●			●	●	●	●	●	●
	anti-HbsAb antibodies	●	●			●			●		
Exploratory											
Serum	Anti-rabies antibodies -(first 50 subjects in Group 4 and Group 5)		●						●		
PBMC	Flow cytometry from all RTS,S vaccinated subjects (Gps 1,2,3)	●	●		●				●		
Transcriptomics	Transcriptomics Groups 1, 2, 3, 4, 5	●	●	●	●				●		

* Study Day for the Study Termination Visit will be the day according to the criteria as specified in section 7.1.1, part E of the protocol being met.

**APPENDIX G. ADULT NORMAL REFERENCE VALUES – KEMRI &
USAMRD-A KISUMU CLINICAL LABORATORIES**

Analyte	Adult Male	Adult Female	Unit	Critical Values	
				Low	High
Creatinine	54.2 - 137.8	52.4 - 96.8	µmol/L	N/A	Male:>248; Female:>174.2
ALT	12.0 - 80.6	10.7 - 61.3	U/L	N/A	Male:>201.5; Female:>153.3
WBC	3.3 - 9.6	3.7 - 9.1	$\times 10^3/\mu\text{L}$	< 2.0	≥ 40.0
HGB	12.6 - 17.2	9.0 - 14.9	g/dL	Male: <8.0; Female: <7.0	>20.0
Platelets	126 - 356	147 - 454	$\times 10^3/\mu\text{L}$	<80	>1000

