Blood sampling for immunologic assays in selected groups of subjects at pre-defined timepoints will be collected as shown in Appendix F. Immunological testing will only be performed in Epoch 3 at visit 35, if required.

E. Study Termination Visit

All participants who have not been withdrawn from the study will complete a Study Termination Visit. The Study Termination Visit will be scheduled once the following criteria have been met:

1. The primary and secondary endpoints have been met; AND
2. All participants have completed Epoch 2.

OR

3. All participants have completed all scheduled visits in Epochs 2 and 3, as applicable (through Visit 35 for Groups 1, 2, 4, and 5; through Visit 27 for Group 3).

The Study Termination Visit will occur within 6 weeks of the above criteria being met. During the Study Termination visit, a whole blood sample for a final cross-sectional parasitemia assessment for PCR and DBS will be collected. This assessment will not contribute to the primary or secondary endpoints.

If the primary and secondary endpoints are not met during the first 6 months ADI and the study has continued into Epoch 3, an additional serology timepoint will be collected at the Study Termination Visit for those subjects in Groups 1, 2, and 3 only. This will be an exploratory endpoint to evaluate the immune response to CS.

The Study Termination Visit may occur at KCRC or as a field visit - see Appendices E and F.

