10.4.3. Analysis of the Secondary Endpoint(s)

Efficacy:

Vaccine efficacy against the first PCR-positive *P. falciparum* infection among adults who were *P. falciparum* negative at baseline will be assessed using Cox proportional hazards regression with a covariate for group assignment to compare Groups 2 and 5. The vaccine efficacy estimates (1-hazard ratio), 95% CI, and p-values will be calculated from this model. Cumulative incidence graphs will also be provided. This analysis will be conducted in the ATP for efficacy cohort.

Immunogenicity:

The primary analysis will be based on the ATP for immunogenicity cohort for analysis of immunogenicity. A secondary analysis based on the TVC will be performed to complement the ATP analysis.

Anti-CS antibodies:

The percentage of subjects with sero-positive levels of anti-CS (proportion of subjects with anti-CS antibody levels with 95% CI) will be determined as shown in Appendix F. Antibody levels after the third dose will also be investigated using reverse cumulative curves.

Anti-HBs antibodies:

The percentage of subjects with sero-positive levels of anti-HBs (proportion of subjects with anti-HBs antibody levels greater than the lower limit of detection/assay dependent) will be determined prior to vaccination, and 14 days post Dose 3. Antibody levels after the third dose will also be investigated using reverse cumulative curves.

Anti-rabies antibodies:

The percentage of subjects in Groups 4 and 5 with sero-positive levels of anti-rabies antibodies will be determined prior to vaccination, and 28 days post Dose 3. Antibody levels after the third dose will also be investigated using reverse cumulative curves.

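### The Study Termination anti-CS sample is secondary and unconditional in Appendix F but exploratory and conditional in 7.1.1 E, and its single calendar date confounds group with time since Dose 3

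*Protocol*

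**What the plan says.** All places are in the protocol.

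- **Status.** Appendix F marks the Study Termination Visit for all four anti-CS rows (NANP and C-term, level and avidity) under the label "Secondary endpoint -Groups 1, 2, 3". Section 4.2.2 defines the secondary anti-CS endpoint by the Appendix F time points, and section 10.4.3 states that the percentage seropositive "will be determined as shown in Appendix F". Section 7.1.1 E says of the same serum: "This will be an exploratory endpoint to evaluate the immune response to CS".
- **Condition.** Section 7.1.1 E takes the serum only if the endpoints were not met in the first 6 months of ADI and the study went on into Epoch 3. Appendix F and section 4.2 give no condition. Appendix E lists the serum for Groups 1 to 3, with a footnote referring to 7.1.1 and Appendix F.
- **Visit.** Section 7.1.1 D states: "Immunological testing will only be performed in Epoch 3 at visit 35, if required". Appendix D has no serum row, and Appendix F has no Visit 35 column. Even so, the cumulative blood volume in Appendix D rises from 260 to 281 mL at Visit 35.
- **Timing.** One trigger applies to the whole study. Either the endpoints are met and "All participants have completed Epoch 2", or "All participants have completed all scheduled visits in Epochs 2 and 3, as applicable". Section 7.1.1 E then says "The Study Termination Visit will occur within 6 weeks of the above criteria being met", and 4.2.3 also gives 6 weeks. Appendix E says the visit "will be completed for all volunteers within 56 days of the set calendar date".

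**The concern.** Every other serum time in Appendix F is a fixed study day, so all subjects are at the same distance from their last dose. The termination sample is not: its study day is left open and depends on when the last subject reaches a given visit. A subject who joined early has waited up to 6 months longer since Dose 3 than one who joined late. A summary for that column is therefore not a result at any one time after vaccination.

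The delay is also unequal across groups. Section 10.5.1 fills Group 3 only from the first parasitemia-positive subjects randomised. Group 3 is the untreated comparison for immune dysregulation, so a later sampling time would push its result in the direction that the study hypothesis expects.

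The conflicting passages raise a separate, practical problem. As written, the site cannot tell whether the sample is due, at which visit or within what window. The window also matters for analysis, because the ATP immunogenicity cohort (10.3.5) requires blood sampling at protocol intervals. A sample on day 50 after the trigger satisfies Appendix E and breaches 7.1.1 E.

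**Working it through.** **Inputs.** Enrolment lasts 6 months (7.1.1 D), or 182.6 days = 26.09 weeks at 30.44 days per month. Visit 2 is day -27. Dose 3 is day 197, Visit 27 day 372 and Visit 35 day 540 (Appendices B, C, D and F). The window is 42 or 56 days. Group 3 takes 35 of the first 105 of 363 parasitemia-positive subjects (10.5.1).

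**Check against the protocol's own durations.**
- No extension: 6 + (27 + 372 + 42)/30.44 = 20.49 months, against 20.5 stated.
- With extension: 6 + (27 + 540 + 42)/30.44 = 26.0 months with the 6-week window, or 6 + (27 + 540 + 56)/30.44 = 26.5 months with the 56-day window, against 26.5 stated.

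The calendar model therefore matches the stated durations.

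**Time since Dose 3 at Study Termination.** The minimum is the last subject enrolled, seen on the trigger date: trigger visit day - 197. The maximum is the first subject enrolled, seen at the end of the window: the minimum plus 26.09 weeks plus the window.

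| Trigger | Minimum | Maximum, 6-week window | Maximum, 56-day window |
|---|---|---|---|
| Last Visit 27 | (372 - 197)/7 = 25.0 wk | 25.0 + 26.09 + 6 = 57.1 wk | 25.0 + 26.09 + 8 = 59.1 wk |
| Last Visit 35 | (540 - 197)/7 = 49.0 wk | 49.0 + 26.09 + 6 = 81.1 wk | 49.0 + 26.09 + 8 = 83.1 wk |

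The spread is 32.1 or 34.1 weeks whichever trigger applies. By contrast, Visit 27 is fixed at 25 weeks, give or take 4 days for the visit itself.

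**Difference between groups** (assumption: even accrual over 6 months within each parasitemia stratum; values at the trigger date, trigger at the last Visit 27).
- The first 105 positives take 105/363 x 26.09 = 7.55 weeks to enrol.
- Group 3: enrolled in weeks 0 to 7.55, mean 3.77. Mean time since Dose 3 = 25 + 26.09 - 3.77 = 47.3 weeks.
- Group 1: 35 subjects enrolled alongside Group 3 (mean 47.3 weeks) and 129 enrolled in weeks 7.55 to 26.09 (mean week 16.82, hence 25 + 26.09 - 16.82 = 34.3 weeks). Overall (35 x 47.3 + 129 x 34.3)/164 = 37.1 weeks.
- Group 2: 25 + 26.09/2 = 38.0 weeks.
- Differences: 47.3 - 37.1 = 10.2 weeks against Group 1, and 47.3 - 38.0 = 9.3 weeks against Group 2. Groups 1 and 2 differ by only about 1 week.

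With a trigger at the last Visit 35, every mean rises by 24 weeks and the differences stay the same.

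**Visit 35 blood volume.** At Visit 27, which has serum (10 mL) and a finger stick, the cumulative total rises by 252 - 241 = 11 mL. At Visit 35, where only a finger stick is scheduled, it rises by 281 - 260 = 21 mL. The schedule shown does not account for that step.

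**The case against.** The strongest reply is that the planned anti-CS analysis is light. Section 10.4.3 plans percent seropositive with confidence intervals and reverse cumulative curves after the third dose. It names no mean titre at Study Termination and no between-group anti-CS test. Presentation by actual time is ordinary analysis-plan detail, Visit 27 already supplies a fixed late time point, and 7.1.1 E already calls the sample exploratory. Much of this stands, and it limits the consequence. It does not remove the conflict over status, visit and window: an analysis plan can choose a summary, but it cannot tell the site whether and when to draw blood.

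A reader might also infer more than the documents support:

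- That titres at this visit would be lowered by a stated percentage. The documents give no antibody half-life, so any such figure is assumed. A drop in titre also does not convert to percent seropositive without the titre distribution.
- That 25 to 59 weeks is the range. It is the extremes of one scenario, and under the condition in 7.1.1 E it is unclear whether the serum would be taken in that scenario. Only the spread is robust.
- That Appendix E contradicts 7.1.1 E on the condition. Its footnote refers to 7.1.1, which softens that conflict. The clear unconditional listing is in Appendix F, whose own footnote cites 7.1.1 E only for the study day.
- That sampling selected on the efficacy outcome is planned, because only event-free subjects from the ADI groups attend Visit 35. No serum is scheduled there. What exists is a stray sentence and an unexplained blood total.

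**Conclusion.** The point holds as an internal contradiction with a limited statistical consequence. The termination anti-CS sample has two statuses (secondary, exploratory), two collection rules (unconditional, only after entry into Epoch 3), two windows (6 weeks, 56 days) and a competing Visit 35 sentence that no schedule supports.

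Taken as Appendix F lists it, the column combines about 32 to 34 weeks of time since Dose 3. Group 3 would be about 9 to 10 weeks later on average than Groups 1 and 2. The spread rests on the planned 6-month enrolment. The group difference also rests on even accrual within each stratum and would shrink or grow with the actual pattern. The direction is clear if antibody wanes: Group 3 would look worse with no true difference. The size in percent seropositive cannot be given, and it could be negligible if nearly all subjects stay above the cut-off.

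The effect is confined to one late immunogenicity time point. A reader should not infer any effect on the efficacy endpoints, the event targets, power or alpha; none of them uses this sample.

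**What to change.** 1. Keep Visit 27 (day 372, 25 weeks after Dose 3) as the last secondary anti-CS time point.
2. Move the Study Termination column of Appendix F to the exploratory part, in line with 7.1.1 E, and say that results there are shown by actual time since Dose 3 and not as one percentage per group. If Group 3 is set against Group 1 at this visit, the 35 Group 1 subjects randomised alongside Group 3 have the same expected timing.
3. State one collection condition for the serum in 4.2, 7.1.1 E, Appendix E and Appendix F.
4. State one window in 4.2.3, 7.1.1 E and Appendix E.
5. Reconcile the Visit 35 immunology sentence in 7.1.1 D with Appendices D and F, and correct or explain the Visit 35 blood total.

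The cost is wording in a few sections and three appendices, plus the change of one late time point from secondary to exploratory. No sample need be lost, and actual time since Dose 3 follows from the dosing and sampling dates that the trial records anyway.
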